 - Alternative hypothesis is that there is significant difference in the proportion of subjects who experience the occurrence of an episode of atrial fibrillation during the infusion protocol when comparing those who receive the isoprenaline infusion with those who receive the placebo infusion.

- Double blinded. Event rate in Isoprenaline group likely >30%. Event rate in placebo group likely <5%. For 90% power and 95% significance projected to need 31 participants per group.
- For higher event rates, fewer participants required. 15 participants per group for event rate >50%, 6 participants per group for event rate >80%.
- Aim to recruit 30 participants per group.

Experiment 3

- Does an infusion of the drug Isoprenaline induce Atrial Fibrillation in subjects following an ablation procedure for common type atrial flutter?
 - Null hypothesis under investigation is that there is no significant difference in the proportion of subjects who experience the occurrence of an episode of atrial fibrillation during the infusion protocol when comparing those who receive the isoprenaline infusion with those who receive the placebo infusion.
 - Alternative hypothesis is that there is significant difference in the proportion of subjects who experience the occurrence of an episode of atrial fibrillation during the infusion protocol when comparing those who receive the isoprenaline infusion with those who receive the placebo infusion.
 - Double blinded. Event rate in Isoprenaline group likely >30%. Event rate in placebo group likely <5%. For 90% power and 95% significance projected to need 31 participants per group.
 - Aim to recruit 35 participants per group.

Experiment 4

- Does an infusion of the drug Isoprenaline induce Atrial Fibrillation in subjects following an ablation procedure for either Atrio-Ventricular Re-entrant Tachycardia (AVRT) or Atrio-Ventricular Nodal Re-entrant Tachycardia (AVNRT)?
 - Null hypothesis under investigation is that there is no significant difference in the proportion of subjects who experience the occurrence of an episode of atrial fibrillation during the infusion protocol when comparing those who receive the isoprenaline infusion with those who receive the placebo infusion.

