 - Alternative hypothesis is that there is significant difference in the proportion of subjects who experience the occurrence of an episode of atrial fibrillation during the infusion protocol when comparing those who receive the isoprenaline infusion with those who receive the placebo infusion.
 - Double blinded. Event rate in Isoprenaline group likely <10%. Event rate in placebo group likely <5%. For 90% power and 95% significance projected to need 133 participants per group.
 - Descriptive data only, not feasible to power properly for this endpoint but may be reasonable to use a 1 sided test. Aim to recruit 35 participants per group.

Experiment 5

- Does a Cavo-tricuspid isthmus ablation for atrial flutter alter inducibility of atrial fibrillation using an isoprenaline infusion?
 - Null hypothesis under investigation is that the proportion of subjects in whom there is a change in the occurrence of atrial fibrillation between two administrations of an infusion of isoprenaline is not less than 20%. Where one administration is before and one is after an atrial flutter ablation procedure.
 - Alternative hypothesis is that the proportion of subjects in whom there is a change in the occurrence of atrial fibrillation between two administrations of an infusion of isoprenaline is less than 20%. Where one administration is before and one is after an atrial flutter ablation procedure.
 - Double blinded, placebo controlled. Event rate >30%
 - A 95%Cl of +/- 10% around an expected % disagreement of 10% would require 35 participants

Experiment 6

- Does an ablation procedure for a AVRT or AVNRT alter inducibility of atrial fibrillation using an isoprenaline infusion?
 - Null hypothesis under investigation is that the proportion of subjects in whom there is a change in the occurrence of atrial fibrillation between two administrations of an infusion of isoprenaline is not less than 20%. Where one administration is before and one is after an SVT ablation procedure.
 - Alternative hypothesis is that the proportion of subjects in whom there is a change in the occurrence of atrial fibrillation between two administrations of an infusion of isoprenaline is less than 20%. Where one administration is before and one is after an SVT ablation procedure.
 - Double blinded, placebo controlled. Event rate <10%
 - A 95%Cl of +/- 10% around an expected % disagreement of 10% would require 35 participants

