Participants will be monitored for at least 30 minutes after the end of the infusion protocol. At this point they will have their basic physiological observations repeated to include pulse rate and rhythm, blood pressure and oxygen saturations. Release from hospital will be at the discretion of the supervising clinician. It is anticipated that a small number of subjects will be required to remain under observation for a number of hours especially in the context of the need for sedation and cardioversion for subjects who remain in persistent arrhythmia following the infusion.

At release from this visit, subjects will be advised to restart any antiarrhythmic agents which they had withheld as part of the study protocol for this visit. They will also be provided with contact information for the study team and advised that they should contact the team with any concerns or problems following their participation in the project. The conclusion of this visit represents the end of their participation in the study.

Study Procedure - Protocol Part B

This part of the protocol involves participants who will have been recruited as they are undergoing an ablation procedure on the NHS. The SVT ablation, atrial flutter ablation and the pulmonary vein isolation groups will be recruited to this part of the study.

The study infusion will be delivered in a double blinded, randomised manner. Each participant group will undergo 1 to 1 randomisation to receive either an isoprenaline infusion at the start and end of their ablation or the placebo infusion at the start and end.

Part B of the protocol will require a minimum of 4 encounters with the study team. For subjects who have given consent to undergo additional ECG monitoring, the study schedule requires 7 visits over the 12 months. Usual NHS care for all participants enrolled to Part B of the protocol would involve 4 visits to hospital, one of these may not be required by the study participants and 3 are combined with study visits.

Schedule for participants involved in Protocol Part B								
Study Procedure	NHS clinical review and / or subsequent telephone conversation	Visit 1 (Enrolment)	Visit 2 (Ablation Procedure)	Visit 3 (6 week F/U)	Visit 4 (3 month F/U)			
Identification of possible suitable subject	x							
Subject given written information and approached about study	x							
Eligibility assessment		х						
Informed Consent		х						
Demographic data collection		х						
Medical history data collection		х						

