If arrhythmia persists for greater than 10 minutes, it will be at the discretion of the attending clinician to decide whether to perform DC cardioversion, continue to wait or to proceed with the intended ablation procedure. If the participant is in persistent arrhythmia at the time of the start of the preablation infusion (most likely to occur in the atrial flutter ablation group) then that infusion will not be performed and the operator will proceed to the ablation procedure. Such participants will receive the post-ablation infusion as per protocol.

After the pre-ablation study drug infusion, the attending clinician will then proceed to the clinically indicated ablation procedure. The diagnosis and endpoint for the ablation procedure will be
recorded. When the attending physician is confident they have achieved their endpoint for the procedure, efforts will be made to induce a similar level of sedation as that recorded at the time of the pre-ablation study drug infusion. It is accepted that this may not be possible in the real world setting.

Once efforts have been made to achieve a similar level of sedation, the post-ablation study drug infusion will be administered using the standard infusion protocol for the identical infusion delivered prior to ablation.

All patients will be expected to leave the cardiac electrophysiology laboratory with a heart rate approaching that seen at baseline (if in sinus rhythm at the start of the procedure) and in sinus rhythm. It is accepted that some patients will require DC cardioversion if atrial fibrillation occurring during the infusion protocol persists for greater than 10 minutes.

It is also anticipated that it may be difficult for participants to tell whether they are undergoing a part of the study protocol or a part of their NHS ablation procedure at any particular time once they have entered the Cardiac Electrophysiology Laboratory. This is due to the use of sedation and the similarity between the participant experience in each part of the procedure. The potential for confusion will be clearly explained in the patient information sheet.

• Part B - Visit 3 – 6 week follow up

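### Experiment 5 makes no allowance for missing before/after pairs: its stated ±10% holds only if no isoprenaline-arm flutter participant is in persistent arrhythmia at the start

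*Protocol*

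**What the plan says.** - **Question and unit.** Study Objectives, Experiment 5, concerns the proportion of subjects with a change between two isoprenaline infusions: "Where one administration is before and one is after an atrial flutter ablation procedure". The null hypothesis is that the proportion with a "change in the occurrence of atrial fibrillation between two administrations of an infusion of isoprenaline is not less than 20" per cent.
- **Size.** The same entry states: "A 95%Cl of +/- 10% around an expected % disagreement of 10% would require 35 participants".
- **Recruitment.** The flutter target stands under Experiment 3: "Aim to recruit 35 participants per group". Study Procedure – Protocol Part B fixes the allocation: "Each participant group will undergo 1 to 1 randomisation to receive either an isoprenaline infusion at the start and end of their ablation", or placebo at both times.
- **Skipped infusion.** Part B – Visit 2 says persistent arrhythmia at the start of the pre-ablation infusion is "most likely to occur in the atrial flutter ablation group) then that infusion will not be performed". It continues: "Such participants will receive the post-ablation infusion as per protocol".
- **Replacement.** Reasons for Discontinuation of Subject's Participation in Study provides a replacement for subjects who withdraw or are excluded, and for no others.
- **Entry rhythm.** The Inclusion Criteria require sinus rhythm on entering the laboratory for Group 4 (pulmonary vein isolation). Group 3 (flutter) has no such criterion.
- **Decision rule.** Sample Size Calculation and Statistical analysis judge disagreement by the upper limit of a one-sided 95% CI, which must lie below 20%. They also give 35 patients.

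**The concern.** A participant contributes to Experiment 5 only with isoprenaline both before and after ablation. Placebo participants do not count, and neither does anyone who missed the first infusion. The protocol expects such misses, mainly in the flutter group, yet sets the required number equal to the full isoprenaline arm. A participant without a first infusion still serves Experiment 3, remains enrolled and triggers no replacement, so nothing in the plan restores the lost pair.

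Two things are at stake. The precision printed under Experiment 5 is one the design delivers only in the best case. And the pairs obtained come only from flutter patients who were not in persistent arrhythmia at the start, whereas the question is put for flutter ablation without that restriction.

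**Working it through.** **Inputs.** Expected disagreement p = 0.10, half-width d = 0.10, 35 participants (Experiment 5). Flutter arm 35, allocation 1:1 (Experiment 3; Part B procedure). Upper limit below 20%, one-sided 95% (Statistical analysis). The share without a pre-ablation infusion is not given, so a range is assumed.

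**1. Reproducing the stated 35.** Two-sided 95% Wald: n = z²p(1−p)/d² = 1.96² × 0.09/0.01 = 34.57, rounded up to 35. This matches, so 35 has no margin.

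**2. Is there a reserve?** Study Duration gives a total of 235. Part A 35 + pulmonary vein isolation 60 (2 × 30) + flutter 70 (2 × 35) + SVT 70 (2 × 35) = 235. No further flutter participants are planned, and the isoprenaline flutter arm is exactly 35.

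**3. Precision by number of complete pairs m, at 10% disagreement.** Two-sided half-width = 1.96 × √(0.09/m). One-sided 95% upper limit = 0.10 + 1.645 × √(0.09/m).

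| Assumed share missing | Pairs | Two-sided half-width | One-sided upper limit |
|---|---|---|---|
| 0% | 35 | 9.9% | 18.3% |
| one pair | 34 | 10.1% | 18.5% |
| 10% | 31 | 10.6% | 18.9% |
| 20% | 28 | 11.1% | 19.3% |
| 30% | 24 | 12.0% | 20.1% |
| 50% | 18 | 13.9% | 21.6% |

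(31.5 and 24.5 are rounded down and 17.5 up; with 17 pairs the half-width is 14.3%.) At 34 pairs the unrounded half-width is 10.08%, so a single lost pair already exceeds ±10%, though trivially.

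**4. The one-sided requirement.** n = 1.645² × 0.09/0.01 = 24.35, rounded up to 25. On this rule 35 − 25 = 10 pairs, or 10/35 = 28.6%, can be lost before the limit at 10% passes 20%. The ±10% statement and the one-sided rule thus need 35 and 25 pairs respectively, yet the protocol attaches 35 to both.

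**The case against.** The strongest reply is that the damage is conditional. No share is given, losing one or two pairs moves the half-width only from 9.9% to 10.1–10.2%, and the protocol's own decision rule tolerates ten lost pairs at 10%. The wording of Experiment 5 can also fairly be read as 35 people with both infusions, which makes the defect a missing allowance and not a false claim. All of this stands, and it sets the size of the point.

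A reader might go further and infer any of the following, which the documents do not support:

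- *That the precision cannot be reached.* It can, if nobody in the arm presents in arrhythmia. The documents do not say how many will.
- *That the one-sided rule collapses below 25 pairs.* Exactly 10% cannot be observed with 24 pairs. Two discordant of 24 gives 0.083 + 1.645 × √(0.083 × 0.917/24) = 17.6%, which passes. At a true 10%, the chance of passing with a Wald limit is 53% with 35 pairs, 46% with 28, 56% with 24 and 45% with 18. There is no cliff, and the course is not monotone because counts are discrete.
- *That skipped infusions ruin an exact analysis.* With an exact limit, 18 pairs pass only with no discordant pair (0.9¹⁸ = 15% at a true 10%). But all 35 pairs pass only 31% of the time, so much of that weakness exists without any loss, and the protocol does not specify an exact interval.

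It can also be said that restricting the pairs to patients not in persistent arrhythmia is inherent, since induction cannot be assessed in someone already in persistent arrhythmia, and that Visit 2 discloses the rule openly. That is fair: it is no design error, but the conclusion of Experiment 5 has to carry the limit.

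**Conclusion.** The point holds in a limited form. The required number of pairs equals the whole isoprenaline flutter arm, the protocol expects some of that arm to yield no pair, it does not replace them, and the total contains no reserve. The ±10% stated under Experiment 5 is therefore a best case presented as the design's precision. The shortfall is small if few present in arrhythmia (10.6% at 10% missing) and appreciable if many do (13.9% at about 50%); these shares are assumptions. Measured by the one-sided Wald rule, the limit at 10% is pushed past 20% only if more than about 29% of pairs are missing. These figures assume Wald limits, the method that reproduces the 35, and disagreement at the planned 10%. Whatever the share, the pairs represent only flutter patients not in persistent arrhythmia at the start.

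**What to change.** 1. Under Experiment 5, define the sample size as isoprenaline flutter participants with both infusions.
2. Replace the fixed ±10% with the precision expected over a stated range of complete pairs, for example 18 to 35 as tabulated, and state the share assumed missing.
3. Reconcile the two-sided ±10% under Experiment 5 with the one-sided rule in Sample Size Calculation and Statistical analysis, and say which one the number 35 serves.
4. Limit the Experiment 5 conclusion to flutter patients not in persistent arrhythmia at the start of the procedure.

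This costs protocol wording only: no extra patients and no change to randomisation or to the infusion procedure. If the sponsor prefers to keep ±10%, flutter recruitment would have to run to 35 complete isoprenaline pairs. That means 35/(1 − share missing) in the isoprenaline arm: 39 at 10%, 44 at 20%, 50 at 30%, and the same number again on placebo. Stratifying the randomisation by rhythm on arrival is not needed for this point: it adds no pairs and would move randomisation to the procedure day.

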- Participants must have a pattern of symptoms and investigation results consistent with a diagnosis of paroxysmal atrial fibrillation

Group 2 – SVT Ablation Group

- Participants must have a history of arrhythmia with documented regular, narrow complex tachycardia available on either 12 lead ECG or ambulatory ECG monitor recording
- Participants must be listed to undergo an Electrophysiology study with a view to performing an ablation procedure
- Participants must go on to have an ablation procedure for either Atrio-Ventricular Re-entrant Tachycardia (AVRT) or Atrio-Ventricular Nodal Re-entrant Tachycardia (AVNRT) with a defined procedural endpoint

Group 3 – Atrial Flutter Ablation Group

- Participants must have a history of arrhythmia with 12 lead ECG documentation fulfilling prespecified criteria for diagnosis of common type (cavotricuspid isthmus dependent) atrial flutter
- Participants must be listed to undergo a cavotricuspid isthmus ablation for common type atrial flutter
- Participants must go on to have only a cavotricuspid isthmus ablation for common type atrial flutter
- Sustained bi-directional cavotricuspid isthmus block must have been demonstrated as the endpoint for the ablation procedure

Group 4 – Pulmonary Vein Isolation Group

- Participants must have a history of arrhythmia with 12 lead ECG or ambulatory ECG monitoring recordings documenting a diagnosis of atrial fibrillation
- Participants must be listed to undergo an ablation procedure for atrial fibrillation with the intent of the attending physician to perform pulmonary vein isolation alone as an ablation strategy
- Participants must be in sinus rhythm at the time that they enter the Cardiac Electrophysiology Laboratory for their ablation procedure.
- Participants must have an ablation procedure for atrial fibrillation and this must have involved only ablation to achieve pulmonary vein isolation
- Pulmonary vein isolation must have been demonstrated as the endpoint for the ablation procedure

Exclusion Criteria

All Participants in All Groups

- Allergy to Isoprenaline
- Any treatment with Amiodarone in the 3 months prior to ablation procedure
- Hypertrophic cardiomyopathy
- Suspected acute myocarditis
- Uncorrected, severe valvulopathy graded by transthoracic echocardiographic parameters
- An Acute Coronary Syndrome within the last 6 months
- Recent (within the last 6 months) or scheduled coronary revascularisation

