- Ongoing angina symptoms without investigations demonstrating the absence of myocardial ischaemia
- Left ventricular ejection fraction measured at <30%
- Symptoms of decompensated heart failure syndrome in the last 3 months
- Severe obstructive lung disease
- Pregnancy at the time of enrolment or a desire to become pregnant during the study period
- Women who are breastfeeding
- Reduced life expectancy not associated with cardiovascular disease (less than 1 year)
- Unable to provide informed consent

Group 1 – Paroxysmal Atrial Fibrillation Group

- Any past history of episode of persistent atrial fibrillation at the time of enrolment to the study
- Treatment with any antiarrhythmic agent within six half-lives of that agent from before an administration of the study drug infusion

Group 2 – SVT Ablation Group

- Any past history of atrial fibrillation documented on 12 lead ECG or ambulatory ECG monitor
- Any past history of atrial flutter documented on 12 lead ECG or ambulatory ECG monitor
- Characterisation of SVT as any arrhythmia other than ANRT or AVNRT
- Treatment with any antiarrhythmic agent within six half-lives of that agent from the ablation procedure (including intra-procedural use) with the exception of isoprenaline and adenosine

Group 3 – Atrial Flutter Ablation Group

- Characterisation of arrhythmia as any arrhythmia other than cavo-tricuspid isthmus dependent atrial flutter at the time of ablation
- Treatment with any antiarrhythmic agent within six half-lives of that agent from the ablation procedure (including intra-procedural use) with the exception of isoprenaline and adenosine

Group 4 – Pulmonary Vein Isolation Group

- Requirement for a more extensive ablation strategy than pulmonary vein isolation alone
- Intra-procedural treatment with any antiarrhythmic agent with the exception of isoprenaline and adenosine
- Treatment with any antiarrhythmic agent in the days before the ablation within six half-lives of that agent from the ablation procedure

Participant Information

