The minimum staff required to administer the infusion will include a registered nurse considered competent with administration of intravenous medications (as judged by the hospital trust at which the infusion is being delivered) and a licensed medical practitioner considered experienced in the field of cardiology and who is a certified Advanced Life Support provider.

Prior to administration of the study drug infusion, the study team will assess the participant regarding their potential suitability for use of antiarrhythmic medications in the event that atrial fibrillation which persists for greater than 10 minutes is induced.

The route of administration will depend on the situation in which the infusion is being administered. Where the infusion is being administered in a ward based environment, it is anticipated that the infusion will be delivered via a peripherally sited intravenous cannula usually sitting in an antecubital fossa vein. Where the infusion is being given in the Cardiac Electrophysiology Laboratory, it will usually be administered via a central venous sheath sited in the femoral vein. Standard aspetic technique associated with the administration of intravenous drugs will be applied in all settings to comply with local policy.

The study drug infusion will be delivered following a modified version of the scheme previously published by Morady and colleagues(30). As their study suggested an accelerating rate of induction up to the maximum dose delivered (20mcg/min), to allow for the potential effect of our study using the sulphate form of the drug rather than the hydrochloride and given the documented favourable tolerability profile of the infusion, we have elected to add a further dose increment to our protocol. This remains within the FDA approved dosing regimen for the drug.

The protocol will be..

- Infusion started at 5mcg per minute for 2 minutes
- Increased to 10mcg per minute for 2 minutes
- Increased to 15mcg per minute for 2 minutes
- Increased to 20mcg per minute for 2 minutes
- Increased to 25mcg per minute for 2 minutes
- Infusion is then stopped and subject is monitored over a 10 minute washout phase

Subjects will either follow the protocol to its completion or will reach one of the pre-defined infusion endpoints at which point the infusion will be stopped. These endpoints as described previously are..

Outcome after which infusion would be stopped

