The investigators are authorised to provide alternative treatment to that specified in the protocol at any stage if he/she feels it is in the participant's best interest. The reasons for deviation from protocol should be recorded.

Reasons for Discontinuation of Subject's Participation in Study

A subject can voluntarily discontinue their involvement in the study at any stage without the need to give reason and without prejudicing further treatment. In addition, subjects will be removed from the study if they cease to meet the inclusion criteria after enrolment (eg participant in SVT block has electrophysiology study that demonstrates atrial tachycardia rather than ANRT or AVNRT) or if they develop one of the exclusion criteria (eg require treatment with amiodarone in the time between the 2 infusions required for Protocol Part A). Subjects will also be excluded from continuation in the study if they develop anaphylaxis, chest pain or ECG features of myocardial ischaemia during the infusion protocol.

Where subjects withdraw or are excluded from the study after enrolment but prior to their completion of the study schedule, a further subject will be recruited to their subject group to take their place. Any data collected before withdrawal may be included in the study results.

End of Study Actions

Having withdrawn from the study, been excluded from continued participation or having completed their final visit or ambulatory ECG recording, participants will have completed their involvement in the study. There are no specific interventions required at completion of the study schedule. All participants will be informed that they may still contact the study team should they have questions or concerns regarding their health or their involvement in the study.

Safety Assessment

Adverse Events

Definitions

- Adverse Event (AE): any untoward medical occurrence in a patient or clinical study subject.
- Serious Adverse Event (SAE): any untoward and unexpected medical occurrence or affect that:
 - Results in death
 - Is life-threatening refers to an event in which the subject was at risk of death at the time of the event; it does not refer to an event which hypothetically might have caused death if it were more severe
 - Requires hospitalisation, or prolongation of existing inpatients' hospitalisation
 - Results in persistent or significant disability or incapacity
 - o Is a congenital anomaly or birth defect

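### Part B removes and replaces participants after randomisation for reasons that can depend on the infusion or the outcome, and leaves the use of their recorded data to choice

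*Protocol*

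**What the plan says.** **Timing.** Study Procedure – Protocol Part B randomises each group 1:1 to isoprenaline or placebo, with the allocated infusion given at the start and at the end of the ablation. Allocation therefore comes before the first infusion and before the ablation.

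**Removal.** Reasons for Discontinuation of Subject's Participation in Study states that "subjects will be removed from the study if they cease to meet the inclusion criteria after enrolment", extends this to anyone who develops an exclusion criterion, and adds that subjects are "excluded from continuation in the study if they develop anaphylaxis, chest pain or ECG features of myocardial ischaemia during the infusion protocol".

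**Replacement and data.** When someone leaves before completing the schedule, "a further subject will be recruited to their subject group to take their place". On their data: "Any data collected before withdrawal may be included in the study results".

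**Criteria that can be judged only after the first infusion.**
- Group 4 inclusion requires of the ablation that "this must have involved only ablation to achieve pulmonary vein isolation". Group 3 has a matching rule for cavotricuspid isthmus ablation.
- Group 4 exclusion: "Intra-procedural treatment with any antiarrhythmic agent with the exception of isoprenaline and adenosine". Groups 2 and 3 exclude antiarrhythmic treatment around the ablation and say that this covers intra-procedural use.

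**Foreseen drug use.** The Infusion Protocol has the team assess each participant before the infusion for "use of antiarrhythmic medications in the event that atrial fibrillation which persists for greater than 10 minutes is induced".

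**The concern.** Randomisation protects the arm comparison only if everyone allocated stays in it, or leaves for reasons unrelated to arm and outcome. Three of the removal triggers arise after the first infusion and could be related to both.

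- An antiarrhythmic given because induced AF persisted would be a direct consequence of the primary outcome.
- Chest discomfort is listed as an expected effect of isoprenaline under Administration of Isoprenaline, so removal for chest pain may be commoner in that arm.
- Ablation beyond the planned lesions is decided by an operator who has just seen, and diagnosed, any induced rhythm.

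Recruiting a replacement restores the head count and makes the loss hard to see. Because use of the removed person's data is optional, the decision can be taken with the results in view.

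**Working it through.** **1. Which outcome is exposed in which experiment.** Study Objectives classes the post-ablation data in the pulmonary vein isolation group as secondary. The primary outcome of Experiment 2 is thus read at the pre-ablation infusion and is already on record when removal could occur. What is at risk there is whether the record is used. Experiments 3 and 4 ask about AF after the ablation. A participant removed after the first infusion has no outcome for them, and an inclusion rule applied later cannot supply one.

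**2. The plan's own sample size.** Inputs from Sample Size Calculation: isoprenaline 30%, placebo 1%, two-sided 5%, 90% power, chi-squared test. With mean proportion 0.155:

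n = [1.96 × √(2 × 0.155 × 0.845) + 1.282 × √(0.30 × 0.70 + 0.01 × 0.99)]² / 0.29² = (1.003 + 0.601)² / 0.0841 = 30.6, so 31 per arm.

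This reproduces the stated 31 (power 90.4%). Experiment 2 aims for 30 per group, which is used below with Fisher's exact test, the plan's choice when counts are small.

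**3. If induced isoprenaline participants are dropped and replaced.** Let f be the fraction of induced isoprenaline participants who are removed, left out of the analysis and replaced. The protocol gives no value, so f is an assumption. The observed rate becomes

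0.30 × (1 − f) / (1 − 0.30 × f)

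For f = 0.20: 0.24 / 0.94 = 25.5%.

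| f | Observed isoprenaline rate | Exact Fisher power, 30 per arm, placebo 1% |
|---|---|---|
| 0 | 30.0% | 86% |
| 10% | 27.8% | 81% |
| 20% | 25.5% | 73% |
| one third | 22.2% | 59% |
| one half | 17.6% | 36% |

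**4. Plausible range of f by the drug route.** The Infusion Protocol expects most induced arrhythmias to revert within 10 minutes. Fewer than half of induced participants would then have an arrhythmia that persists, so f = one half is beyond what the protocol's own expectation allows. For f = one third, more than two thirds of the persisters (0.333 / 0.5 = 0.67) would need a drug. One third is therefore near the upper bound, and values near zero are also compatible with the text.

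**5. The opposite direction.** Suppose a fraction g of non-induced isoprenaline participants is dropped and replaced, for example for chest pain before any AF. The observed rate becomes 0.30 / (1 − 0.70 × g): 32.3% for g = 10%, 34.9% for 20% and 38.0% for 30%. The isoprenaline rate is then inflated.

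**6. If recorded data are always used.** f and g are zero for Experiment 2, the rate stays at 30% v 1%, and no change in sample size is needed. Missing post-ablation outcomes in Experiments 3 and 4 remain.

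**The case against.** The strongest reply is that the protocol does not discard anything. It stops people continuing and allows earlier data to be used, and the Experiment 2 outcome is recorded before removal can happen. This stands as far as it goes. A reader might infer that the protocol deletes events, but the text permits that without ordering it. The defect is the discretion.

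Second, the drug route is less settled than the Infusion Protocol suggests. For arrhythmia beyond 10 minutes after the pre-ablation infusion, Part B – Visit 2 lists cardioversion, waiting or proceeding to ablation, and no drug. This also stands: the sections disagree, and how often the route would occur cannot be known.

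Third, a reader might infer that the infusion causes extra ablation. No section says so. Group 4 enrols on a prior intention to isolate the pulmonary veins only, and operators are blinded to allocation. A link is possible because the operator sees the rhythm, but it is not stated.

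Fourth, not every removal depends on arm. The protocol's own examples are a tachycardia found to be of another type, and amiodarone needed between the two Part A infusions. Neither is a Part B drug or outcome effect, so a sound fix must separate an ineligible diagnosis from later events.

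Fifth, the chest pain rule is a safety rule about continuing, and the protocol calls such effects uncommon. That is a fair reading, but the rule still removes the post-ablation outcome and triggers a replacement.

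Finally, analysis sets are often left to a statistical analysis plan, which is not at hand. Such a plan could fix the sets. However, removal, replacement and the optional use of data are operative protocol text, and no analysis plan can recover the outcome of an infusion that was not given.

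**Conclusion.** The point holds in limited form. The protocol allows removal and replacement after randomisation for reasons that can depend on arm and outcome, and sets no rule for the data already recorded. The comparison set in Experiments 2, 3 and 4 can therefore be chosen after results are known, and Experiments 3 and 4 can lose outcomes selectively.

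The size is uncertain. On the assumption that 10% to 20% of induced isoprenaline participants are dropped and replaced, Experiment 2 would observe 27.8% to 25.5% in place of 30%, with Fisher power of 81% to 73% against 86%. One third (22.2%, 59%) is close to the most the protocol's expectations allow. A reader might infer a fixed bias toward no effect. The documents do not support that, since losing intolerant, non-induced participants would raise the isoprenaline rate.

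**What to change.** Amend the protocol as follows.

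- **Recorded data.** State that data collected before withdrawal *will* be included.
- **Experiment 2.** Analyse, in the allocated arm, every randomised Group 4 participant whose pre-ablation infusion was started, whatever ablation or drug followed.
- **Experiments 3 and 4.** Analyse every randomised participant with the eligible diagnosis (common type flutter; AVRT or AVNRT). Exclude only for a diagnosis that predates randomisation and is judged blind to arm. Report by arm who did not receive the post-ablation infusion and why, with sensitivity analyses counting them once as induced and once as not induced.
- **Removal from analysis.** Treatment given after an infusion-induced arrhythmia is not a reason for it. Stopping further infusions for safety is a separate matter and is unaffected.
- **Replacement.** Only for participants who leave before their first infusion or are found to have an ineligible diagnosis.
- **Reconciliation.** The Exclusion Criteria for Groups 2 to 4, the Infusion Protocol and Part B – Visit 2 must be made consistent on antiarrhythmic use after an induced arrhythmia. Which clinical rule applies is for the investigators.

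The cost is amendment wording, with no change in sample size. The one drawback is that some post-ablation infusions will be analysed with residual drug effect or after extra ablation, which a sensitivity analysis can show.
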